6.2 SECONDARY

The secondary objective is to evaluate efficacy, safety and quality of life in pediatric patients with allergic rhinoconjunctivitis treated with Lertal[®]. The secondary endpoints are the following:

- Overall symptom control assessed by means of a VAS after 2 and 4 weeks of treatment.
- Change from baseline of the Total Symptom Score (TSS) after 2 weeks of treatment.
- Number of responders (at least 30% reduction of TSS) after 2 and 4 weeks of treatment.
- Time to maximum effect on TSS vs placebo.
- Use of “rescue treatment.”
- Change from baseline of Total Nasal Symptom Score (TNSS) after 2 and 4 weeks of treatment.
- Change from baseline of Total Ocular Symptom Score (TOSS) after 2 and 4 weeks of treatment.
- Change from baseline of Total Throat Symptom Score (TTSS) after 2 and 4 weeks of treatment.

- Issues interfering with quality of life at Baseline (Week 0), after Period I (Week 4) and after Period II (Week 8 o Week 16).
- Number of patients symptom-free or with mild symptoms during Period I.
- Number, intensity and duration of exacerbations during Period II. Exacerbations are defined as the need of an antihistamine medication of any kind, at any dose and of any duration.

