8.1 INCLUSION CRITERIA

Each patient must meet all of the following inclusion criteria:

- Age 6 to 12 years
- Male or female
- Diagnosis of allergic rhinoconjunctivitis

- Hypersensitivity to dust mites or pollen confirmed with skin-prick test (wheal and redness, ≥ 3 mm more extended than control) performed in the previous 12 months
- Total Symptoms Score (TSS) ≥ 15 and at least 1 for nasal congestion
- Written informed consent of patient and of parent or legal guardian

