10 ASSESSMENTS

10.1 EFFICACY ASSESSMENTS

10.1.1 Total Symptom Score

The primary variable of the study is the Total Symptoms score (TSS), a patient-reported evaluation of nine symptoms:

- Nasal symptoms (TNSS): itching, sneezing, rhinorrhea, nasal congestion
- Ocular symptoms (TOSS): itching, hyperemia of conjunctiva, tearing
- Throat symptoms (TTSS): itching, coughing

With the help of their parents, patients will score symptoms on a 4-point scale: 0 = absent or irrelevant, 1 = mild, 2 = moderate, 3 = severe.

TNSS is the sum of the scores of nasal symptoms, TOSS the sum of the scores of ocular symptoms and TTSS the sum of throat symptoms.

TSS is calculated as the sum of TNSS, TOSS and TTSS.

At baseline (Visit 2), Visit 3 and Visit 4, and with the help of a parent, patients are asked to assign a score to the symptoms experienced in the last 12 hours and over the previous two weeks.

The overall TSS score is derived as the mean of the two TSS scores related to the symptoms experienced in the last 12 hours and over the previous two weeks.

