- Change from baseline of VAS score after 2 and 4 weeks of treatment. The between-group analysis will be performed by means of a t-test for independent samples or analogous non-parametric test.

- Changes from baseline of TSS scores after 2 weeks of treatment. The between-group analysis will be performed by means of a t-test for independent samples or analogous non-parametric test.
 - Changes from baseline of TSS score for each patient after 2 and 4 weeks of treatment will be classified as $\geq 30\%$ and $< 30\%$, thus defining responder and non-responder patients. Between-group differences will be tested by means of a Chi-square test with 2x2 contingency tables.
 - Time to maximum effect on TSS vs placebo will be analysed by means of t-test for independent samples after log-transformation of the data or analogous non-parametric test.
 - Between-group differences in the number of patients using rescue treatment will be analyzed by means of a Chi-square test with 2x2 contingency tables.
 - Changes from baseline in TNSS, TOSS and TTSS scores will be calculated after 2 and 4 weeks of treatment and between-group differences analyzed by means of a t-test for independent samples or analogous non-parametric test.
 - The number of patients with score for a single symptom ≤ 1 will be calculated and the between-group differences analyzed by means of a Chi-square test with 2xn contingency tables, where n represents the number of observations.
 - The intensity of the onset of exacerbations occurring during Period II will be evaluated through the TTS score and compared between the two groups using a t-test for independent samples or analogous non-parametric test.
 - The between-group differences in the number and duration of exacerbations occurring during Period II will be analyzed by means of a Mann-Whitney U test.
- **Quality of life**

Changes from baseline of the PRQLQ total score will be calculated at the end of Period I (Week 4) and end of Period II (Week 8 or Week16). An analysis of variance for repeated measures will be adopted, isolating the variability due to type of allergy, treatment group, time of observation and their interaction.

- **Safety**

All safety analyses will be performed on the Safety set. No missing data handling approach will be applied.

Results of physical examinations at each assessment will be presented.

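### The symptom-free-or-mild endpoint is tested by an unadjusted chi-square, although many children may already be at 1 or less on a symptom at entry; stratify by that symptom's baseline score

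*Combined protocol and SAP*

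**What the plan says.** Section 6.2 lists the endpoint as "Number of patients symptom-free or with mild symptoms during Period I". Section 13.2.2 and the synopsis give its only working definition: "The number of patients with score for a single symptom" of 1 or less, with groups compared by a "Chi-square test with 2xn contingency tables, where n represents the number of observations". Neither place restricts the denominator, requires a shift from baseline or adjusts for the baseline item score. Efficacy is analysed in the ITT population (section 13.2.1).

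Section 10.1.1 describes the TSS as "a patient-reported evaluation of nine symptoms", each scored "0 = absent or irrelevant, 1 = mild, 2 = moderate, 3 = severe". A score of 1 or less therefore means absent or mild. The scores are collected at Visits 2, 3 and 4. Section 8.1 sets entry at "Total Symptoms Score (TSS) ≥ 15 and at least 1 for nasal congestion"; no other symptom has a minimum of its own.

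**The concern.** Eligibility is set on the total, while the endpoint is set on single items. A child can enter with a high total and still be at 0 or 1 on several symptoms. For congestion, the one symptom with an entry minimum, that minimum is itself a score that meets the endpoint. Children who start mild and stay mild count as successes in both groups.

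Two things are at stake. The first is interpretation: a high proportion with mild or no symptoms may be taken as the result of treatment when part of it was there at randomisation. The second is precision: baseline item status is likely to predict the outcome strongly, and the planned test makes no use of it.

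**Working it through.** **Plan's own figure.** The documents give no power or response rate for this endpoint. The only sample-size figure is for the primary endpoint: 72 per group, effect size 0.47, two-sided 5%. A t-test calculation returns 80.0% power, so the figure reproduces. I use 72 per arm below.

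**How many symptoms can already be at 1 or less.** With k of nine items at 1 or less, the highest possible total is k × 1 + (9 − k) × 3 = 27 − 2k. The condition 27 − 2k ≥ 15 gives k ≤ 6. Example: six items at 1 and three at 3 make 6 + 9 = 15. The bound also holds if item scores are averaged over the 12-hour and two-week recalls.

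**How common this might be.** Enumerating all 4⁹ integer score patterns leaves 86,530 that meet the entry rule; 99.4% of them have at least one item at 1 or less. The item weights below, with items independent before the entry rule is applied, are assumptions and not forecasts.

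| Assumed weights for scores 0/1/2/3 | Mean items ≤ 1 | Congestion ≤ 1 | Any other given symptom ≤ 1 |
|---|---|---|---|
| 0.25/0.25/0.25/0.25 | 3.13 | 24% | 36% |
| 0.10/0.25/0.35/0.30 | 2.62 | 24% | 30% |
| 0.05/0.20/0.45/0.30 | 2.02 | 19% | 23% |

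**Effect on the comparison.** Let b be the share already at 1 or less. Assume success from a baseline of 2 or more is 65% vs 42%, and let m₁ and m₀ be the shares of already-mild children who stay at 1 or less on active and placebo. The difference in all children is (1 − b)(0.65 − 0.42) + b(m₁ − m₀). With b = 0.30 and m₁ = m₀ = 0.95:

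- active: 0.285 + 0.455 = 74.0%
- placebo: 0.285 + 0.294 = 57.9%
- difference: 16.1 points, against 23 among children starting at 2 or more.

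**Power of three analyses.** Each line is 200,000 simulated trials with 72 per arm, two-sided 5%. The unadjusted test and the Cochran-Mantel-Haenszel (CMH) test use all children; the CMH test is stratified by baseline item score (1 or less vs 2 or more). The restricted test uses only children starting at 2 or more.

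| Stay mild (active vs placebo) | b | Unadjusted | CMH | Restricted |
|---|---|---|---|---|
| 95% vs 95% | 20% | 62.5% | 68.0% | 70.3% |
| | 30% | 53.1% | 60.9% | 64.8% |
| | 40% | 44.3% | 52.5% | 57.8% |
| 90% vs 90% | 20% | 62.5% | 66.6% | 70.6% |
| | 30% | 52.2% | 58.2% | 64.7% |
| | 40% | 42.5% | 48.5% | 57.8% |
| 95% vs 90% | 20% | 67.0% | 71.8% | 70.3% |
| | 30% | 60.2% | 67.2% | 64.7% |
| | 40% | 54.2% | 61.9% | 57.9% |
| 95% vs 85% | 20% | 71.5% | 75.4% | 70.4% |
| | 30% | 67.0% | 73.0% | 64.7% |
| | 40% | 63.6% | 70.4% | 57.9% |
| 90% vs 80% | 20% | 71.2% | 73.8% | 70.5% |
| | 30% | 66.0% | 70.3% | 64.4% |
| | 40% | 61.7% | 66.8% | 57.9% |

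CMH beats the unadjusted test in all 15 lines, by about 3 to 8 points. The restricted test is best when treatment does nothing for already-mild children, and falls below the unadjusted test when it helps keep them mild by 10 points. With no treatment effect, in six scenarios, CMH rejected in 4.9 to 5.0% of trials and the unadjusted test in 4.8 to 5.5%.

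**The case against.** Section 6.2 names a status, not a change, and how many children have a symptom under control on each treatment is a fair question. Improvement is covered elsewhere, by change in TSS, TNSS, TOSS, TTSS and VAS and by the 30% responder rate. This stands: the endpoint need not be turned into a shift from baseline.

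A reader might infer that counting already-mild children biases the comparison. The documents do not support that. Allocation is randomised 1:1, so these children are balanced in expectation, and chance imbalance is ordinary sampling error that the test allows for.

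A reader might also infer that the endpoint should be limited to children starting at 2 or more, because the larger difference must outweigh the smaller sample. The table shows that this depends on what treatment does for already-mild children, on which the documents are silent. Restriction also gives each symptom its own denominator, leaves the ITT population and hides children who worsen from mild.

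The reading itself is open to doubt. If the endpoint meant all nine symptoms at 1 or less, the total could be at most 9 and no eligible child would meet it at entry. Section 13.2.2 says a single symptom, however, so the per-symptom reading is the one its wording supports. That section also defers further detail to a SAP document; nothing in the documents at hand changes this definition.

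**Conclusion.** The point holds as a missed adjustment and a reporting gap in one secondary endpoint. That up to six of nine symptoms can already meet the endpoint at entry follows directly from the plan's own rules. How many children this concerns, and the gain of about 3 to 8 power points, rest on assumed item distributions and response rates (65% vs 42%, 20 to 40% already mild, 80 to 95% staying mild). The direction of the gain was the same in every scenario tried. The documents do not support calling the planned comparison invalid or the endpoint misconceived. The sample size was set for the TSS change, and the primary analysis is unaffected.

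**What to change.** In section 13.2.2 and the synopsis, state that for each symptom, at Week 2 and at Week 4, the proportion scoring 1 or less is compared in all ITT children by a Cochran-Mantel-Haenszel test stratified by that symptom's baseline score (1 or less vs 2 or more). Report the proportions by group within each baseline stratum, so that the result among children starting at 2 or more appears as supportive. State also whether the 12-hour score, the two-week score or their mean is used for the item.

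The cost is a few lines of SAP text and one extra table layout. The baseline item scores are already collected at Visit 2, no child is dropped, and the sample size does not change.

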13.1 DETERMINATION OF SAMPLE SIZE

160 patients are to be enrolled in this study.

Confidential

A sample of 72 patients for each group will have an 80% power to detect an effect size on the primary variable ($\delta = |\mu_1 - \mu_2| / \sigma$) of 0.47 (medium effect size) (12), using an independent samples t-test with a two-tailed significance level of 5%.

A sample size of 80 patients per group will account for an expected dropout rate of 12% (13), using Freedman's formula (*Control Clin Trials*, 1990): $n' = 100 * n / 100 - x$, where x is the expected dropout rate.

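### The secondary endpoint of children who are symptom-free or mild describes the whole child, but its only analysis rule limits the score of a single symptom and leaves the other eight unconstrained

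*Combined protocol and SAP*

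**What the plan says.** Section 6.2 and the synopsis list this secondary endpoint: "Number of patients symptom-free or with mild symptoms during Period I". Section 10.1.1 describes the TSS as "a patient-reported evaluation of nine symptoms", with each item scored "0 = absent or irrelevant, 1 = mild, 2 = moderate, 3 = severe".

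The matching line in Section 13.2.2, repeated in the synopsis under statistical considerations, is: "The number of patients with score for a single symptom ≤ 1 will be calculated". The test given for it is a "Chi-square test with 2xn contingency tables, where n represents the number of observations".

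The line does not say which symptom is meant, or whether the limit applies to any symptom, to each in turn, or to every one. It names no visit. It also names no recall window, although Section 10.1.1 has each symptom scored twice per visit: "patients are asked to assign a score to the symptoms experienced in the last 12 hours and over the previous two weeks".

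**The concern.** The endpoint is one of disease control: how many children have nothing worse than mild symptoms. A limit on one symptom cannot show that, because it says nothing about the remaining eight. Depending on how the line is programmed, the reported count could include children with severe disease, or the count might not be produced at all. The reader of the results would still see it under a label that suggests control of the whole condition.

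Timing adds to this. Section 7.1 lets sites unblind each child once Period I data entry is complete, and Section 9.5.1 keeps data analysts blinded only until the end of Period I. A choice between the readings made after that point would be open to influence from the data.

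**Working it through.** **The plan's own figure.** No figure is given for this endpoint. The only powered figure is for the primary endpoint: "A sample of 72 patients for each group will have an 80% power". With a standardised effect of 0.47 and two-sided 5%, n = 2 × (1.960 + 0.842)² / 0.47² = 71.1, so 72 per group. The t-test power at 72 is 79.98%. The figure reproduces and has no bearing on this point.

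**Does the analysis line belong to this endpoint?** Section 13.2.2 does not repeat the endpoint's name, so the link is inferred, but it is well supported:
- A score of 1 or less is exactly absent or mild on the item scale.
- In the synopsis, both the endpoint and the line come after the nasal, ocular and throat scores and before exacerbations.
- No other analysis line fits the endpoint, and no other endpoint fits the line.

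**Inputs for the check.** Nine items, each scored 0 to 3 (Section 10.1.1), and the entry condition in Section 8.1: "Total Symptoms Score (TSS) ≥ 15 and at least 1 for nasal congestion". The enumeration takes integer scores from one recall window.

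**Reading 1: any one symptom at 1 or less.**
- Highest TSS that still counts: 8 × 3 + 1 = 25, out of 9 × 3 = 27.
- All possible profiles: 4⁹ = 262,144. Of these, 86,530 meet the entry condition.
- A profile fails the rule only if every item is 2 or 3. There are 2⁹ = 512 such profiles, and all meet entry because their sum is at least 9 × 2 = 18.
- Entry-eligible profiles that already satisfy the rule: 86,530 − 512 = 86,018, and 86,018 / 86,530 = 99.4%.

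Under this reading the rule hardly separates children at entry severity from children who are well.

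**Reading 2: each symptom tabulated separately.**
- This gives nine between-group comparisons per visit. If they were independent at 0.05, the chance of at least one false positive would be 1 − 0.95⁹ = 0.37. Symptoms are likely to be correlated, which would generally lower that figure.
- Nine separate counts do not determine the patient-level count. As an illustration, suppose each symptom is mild in half the children. These could be the same children throughout, so that half are mild on everything. Or half could be mild on four symptoms only and the other half on the remaining five only, so that no child is mild on everything.

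**Reading 3: every symptom at 1 or less.**
- Highest TSS that counts: 9 × 1 = 9. No entry-eligible profile qualifies, since entry needs at least 15.
- This reading gives the named endpoint, but the text does not state it.

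**The table shape.** The responder and rescue analyses, which are yes/no per child, use 2x2 tables. This line uses 2xn. That fits several symptoms, or several visits, at least as well as one flag per child. Since n is explained only as the number of observations, the table does not settle the reading.

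**The case against.** The strongest reply is that the line is ambiguous rather than wrong. It nowhere says that any one symptom is enough, and the 2xn table suits per-symptom tabulation at least as well. At a stretch it can mean every symptom. Section 6.2 names the state without defining it, and Section 13.2.2 defers further detail to a Statistical Analysis Plan document that is not part of the text available here.

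Much of this stands. A reader might infer that the plan has adopted the any-one rule; the wording permits that but does not establish it. The objection does not remove the mismatch, because both natural readings miss the named endpoint and only the least natural one delivers it. A promise of further detail does not correct a rule already written down.

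Two further inferences should be resisted:
- A reader might conclude that both arms would sit near the ceiling at Week 4. The documents give no item-level distribution, and the 99.4% describes possible profiles at entry, not children after four weeks of antihistamine in both arms.
- A reader might conclude that every child with a TSS of 15 to 17 must qualify under the any-one rule, since nine items at 2 sum to 18. That holds for integer scores in one window only, whereas the overall TSS is the mean of two windows. Take two-week items all at 2 (total 18), and 12-hour items with five at 1 and four at 2 (total 13). The overall TSS is (18 + 13) / 2 = 15.5. No two-week item is at 1 or less, and the item means are 1.5 or 2. The answer depends on a window that the line does not specify.

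**Conclusion.** The point holds as a mismatch between a patient-level endpoint and a single-symptom rule. Under the any-one reading, a child with TSS 25 of 27 can be counted as symptom-free or mild, and 86,018 of 86,530 entry-eligible profiles (99.4%) qualify before treatment. Under the per-symptom reading, the named count is never computed and nine tests take its place.

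This rests on two assumptions: that the single-symptom line is the analysis of this endpoint, and, for the profile counts, that integer scores from one recall window are used. Which reading was intended cannot be determined from the text, and the conclusion does not depend on it. The endpoint is secondary and unpowered, and the primary analysis is unaffected. The wording should be corrected before any unblinding.

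**What to change.** In Section 13.2.2 and the matching synopsis line, replace the single-symptom rule with a patient-level one: a child is symptom-free or mild at a visit if all nine TSS item scores are 1 or less in a stated recall window. The previous-two-weeks score is one candidate. With visits two weeks apart, it would cover Period I across Weeks 2 and 4. Whichever window is chosen, fix it before unblinding.

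Compare the arms on this count at Week 4, and separately at Week 2, with a 2x2 chi-square test. The existing rule that treats children who interrupt treatment as failures on qualitative variables can then be applied directly. Label per-symptom frequencies as descriptive.

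Requiring all nine symptoms is one choice of definition; the documents do not dictate it. If the sponsor prefers another, it should be written out with the same precision.

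The cost is wording only, since the item scores are already collected at Visits 2, 3 and 4. The downside is that fewer children will meet the stricter state. The sample size does not change.

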	
whereas safety will be evaluated in the Safety population.
 
• Primary endpoint 
Changes from baseline of TSS scores will be calculated after 4 weeks of treatment. The between-group analysis will be performed by means of a t-test for independent samples or analogous non-parametric test.
 
• Secondary endpoints 
○ Change from baseline of VAS score after 2 and 4 weeks of treatment. The between-group analysis will be performed using a t-test for independent samples or analogous non-parametric test.○ Change from baseline of TSS scores after 2 weeks of treatment. The between-group analysis will be performed by means of a t-test for independent samples or analogous non-parametric test.○ Change from baseline of TSS score for each patient after 2 and 4 weeks of treatment will be classified as $\geq 30\%$ and $< 30\%$, thus defining responder and non-responder patients. Between-group differences will be tested by means of a Chi-square test with 2x2 contingency tables.○ Time to maximum effect on TSS vs placebo will be analysed by means of t-test for independent samples after log-transformation of the data or analogous non-parametric test.○ Between-group differences in the number of patients using rescue treatment will be analyzed by means of a Chi-square test with 2x2 contingency tables.○ Changes from baseline in TNSS, TOSS and TTSS scores will be calculated after 2 and 4 weeks of treatment and between-group differences analyzed using a t-test for independent samples or analogous non-parametric test.○ The number of patients with score for a single symptom ≤ 1 will be calculated and the between-group differences analyzed by means of a Chi-square test with 2xn contingency tables, where n represents the number of observations.○ The intensity of the onset of exacerbations occurring during Period II will be evaluated through the TTS score and compared between the two groups using a t-test for independent samples or analogous non-parametric test.○ The between-group differences in number and duration of exacerbations occurring during Period II will be analyzed by means of a Mann-Whitney U test. 
• Quality of life
--	--

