11 STUDY PROCEDURES

11.1 VISIT SCHEDULE

The visit schedule consists of 6 visits. V1 and V2 (baseline) take place during the run-in period, V3 and V4 during the 4 weeks of Period I, and V5 and V6 (only for patients allergic to dust mites) during the 4 weeks or 12 weeks (only for patients allergic to dust mites) of Period II.

At V1 (Week -2), after having obtained signed informed consent from the patient, the Investigator will gather demographic and medical history data. The Investigator will perform a physical examination and evaluate the patient's eligibility for the study according to the inclusion/exclusion criteria indicated in [Section 8](#).

At V2 (Week 0), each patient will be randomized to one of two treatments (Lertal[®] + standard therapy or placebo + standard therapy) and will be provided with enough product to last until Visit 4. The Investigator will perform a physical examination, and the patient will be asked to complete the patient reported outcomes (TSS, TNSS, TOSS, TTSS, VAS, PRQLQ). The Investigator will also enquire about any adverse events the patient may have experienced and about any concomitant medication the patient may have taken since Visit 1. The patient will be given a diary.

Visit 1 and Visit 2 may be performed on the same day.

V3 (Week 2), V4 (Week 4): The patient will be asked to complete the patient reported outcomes (TSS, TNSS, TOSS, TTSS, PRQLQ, VAS) and the Investigator will also enquire about any adverse events the patient may have experienced and about any rescue/concomitant medication the patient may have taken since the previous visit. A physical exam will be performed at V4. The diary should be returned at these visits for review by the Investigator. The patient should also return unused product at each visit.

V5 (Week 8), V6 (Week 16 – only for patients allergic to dust mites): The patient will be asked to complete the quality of life questionnaire (PRQLQ) and the Investigator will also enquire about any adverse events/exacerbations the patient may have experienced and about any rescue/concomitant medication the patient may have taken since the previous visit. A physical exam will be performed at V5 or V6. The diary should be returned at these visits for review by the Investigator.

See the assessment chart in [Section 2.2](#) for details regarding the visit schedule and assessments and [Section 10](#) for information concerning the assessments.

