13.2.2 Statistical Analysis

All data collected in the study will be listed and summarized as appropriate as described below. Continuous data will be summarized by means of common descriptive statistics: mean, standard deviation (SD), median, first and third quartiles, minimum and maximum. Categorical data will be presented by absolute and relative frequencies (n and %) or contingency tables.

For the safety analysis, patients will be included in based on available assessments; no missing data handling approach will be applied. For efficacy analyses, patients who interrupt treatment will be considered as “failures” for qualitative variables and their missing quantitative data will be substituted according to the LOCF method (Last Observation Carried Forward). Unless stated otherwise, two-sided p-values <0.05 will be considered statistically significant.

All statistical tables, listings, figures and analyses will be generated using SAS® release 9.4 or later (SAS Institute Inc., Cary NC, USA).

No interim analyses are planned.

Further details about data analysis will be provided in the Statistical Analysis Plan document.

All data about patient demographics and baseline characteristics will be summarized on the ITT population by treatment group by means of summary descriptive statistics.

The number and percentages of subjects meeting all eligibility criteria at screening will be provided. The analysis populations will be described and the reasons for excluding a patient from any particular population will be provided with the number of protocol deviators per each criterion.

A complete description of patients’ disposition will be provided specifying the number of randomized patients, the number of patients at each visit, the number of completed and discontinued patients and the reason for the discontinuation.

Medical history data will be presented by Medical Dictionary for Regulatory Activities MedDRA dictionary system organ class (SOC) and preferred term (PT).

Concomitant medications and significant non-drug therapies will be presented by WHO Drug Dictionary ATC class and preferred term.

- **Primary endpoint**

Changes from baseline of TSS scores will be calculated after 4 weeks of treatment. The between-group analysis will be performed by means of a t-test for independent samples or analogous non-parametric test.

- **Secondary endpoints**

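### The symptom-free-or-mild endpoint is assigned a chi-square on an undefined 2×n table; on its most direct reading the test does not compare the proportion of children reaching a score of 1 or less

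*Combined protocol and SAP*

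**What the plan says.** Section 6.2 lists the endpoint as "Number of patients symptom-free or with mild symptoms during Period I", a patient-level count with no week attached. The analysis in the synopsis reads: "The number of patients with score for a single symptom ≤ 1 will be calculated and the between-group differences analyzed". Section 13.2.2 uses the same sentence and completes it with the test: "analyzed by means of a Chi-square test with 2xn contingency tables, where n represents the number of observations".

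Five other places bear on how to read this:

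- Section 11.1 puts "V3 and V4 during the 4 weeks of Period I", so Period I has two post-baseline assessments, at Weeks 2 and 4.
- The quality-of-life paragraph of Section 13.2.2 speaks of "isolating the variability due to type of allergy, treatment group, time of observation and their interaction", which suggests that an observation is a visit.
- For responders, Section 13.2.2 says: "Between-group differences will be tested by means of a Chi-square test with 2x2 contingency tables". Rescue use also gets a 2×2 table.
- Sections 13.2.1 and 13.2.2 carry a missing-data rule: "patients who interrupt treatment will be considered as “failures” for qualitative variables".
- Section 10.1.1 defines nine symptoms scored 0 to 3 and says "patients are asked to assign a score to the symptoms experienced in the last 12 hours and over the previous two weeks". Sections 10.1.1 and 10.1.2 define a mean of the two recall scores for the totals (TSS, TNSS, TOSS, TTSS), but not for a single symptom.

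**The concern.** The endpoint asks how many children in each arm became symptom-free or mild. That question needs a table showing, for each arm, how many children reached the state and how many did not. The plan names a different table. Its columns are counted by observations, which could be visits, symptoms or recall windows, and no column for children who did not reach the state is mentioned. The responder and rescue endpoints in the same list each get an explicit 2×2, so the departure here is not a shared shorthand.

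The status itself is also open. The endpoint is per patient, but the analysis refers to a single symptom, and two recall scores exist for each. A child scoring 1 for the last 12 hours and 2 for the previous two weeks passes on the first, fails on the second and fails on their mean of 1.5. A child scoring 0 and 2 passes on the mean of 1 but fails on the two-week score.

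At stake is whether this endpoint's p-value answers its own question, and whether the choice of table is fixed before the data are seen.

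**Working it through.** **The plan's own figure.** The documents give no rate, power or sample size for this endpoint. The only related figure is the primary sample size in Section 13.1: n = 2(1.96 + 0.8416)² / 0.47² = 15.70 / 0.2209 = 71.1, rounded up to 72 per group. This reproduces the stated 72. The 80 per group and 12% dropout from that section are used below as inputs only.

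**Algebra, no rates needed.** Take rows = arms, columns = observations, cells = children at 1 or below, a_j in one arm and b_j in the other, with sums A and B. The expected count in the first arm is A(a_j + b_j)/(A + B). If a_j = k·b_j in every column, this equals kB(k + 1)b_j / ((k + 1)B) = k·b_j = a_j. Every residual is zero, so chi-square = 0 and p = 1 for any k. The number of children per arm does not enter the statistic. A child at 1 or below at both visits is counted in both columns, so the counts are not independent.

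**Worked tables.** Assumed counts, 80 per arm, no dropout, Pearson chi-square without continuity correction:

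| Assumed % at ≤1, Week 2/Week 4 | Direct 2×n reading | 2×2 at Week 4 |
|---|---|---|
| 50/50 vs 25/25 | [[40,40],[20,20]]: 0.00, p = 1.00 | [[40,40],[20,60]]: 10.67, p = 0.0011 |
| 30/60 vs 15/30 | [[24,48],[12,24]]: 0.00, p = 1.00 | [[48,32],[24,56]]: 14.55, p = 0.00014 |
| 40/60 vs 20/40 | [[32,48],[16,32]]: 0.57, p = 0.45 | [[48,32],[32,48]]: 6.40, p = 0.011 |
| 40/70 vs 40/40 | [[32,56],[32,32]]: 2.83, p = 0.093 | [[56,24],[32,48]]: 14.55, p = 0.00014 |

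Nine symptom columns behave the same way: 60 against 30 of 80 on every symptom gives 0 on 8 df, p = 1.

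**Rejection rates, two-visit reading only.** These come from 20,000 simulated trials per scenario and setting, two-sided 5%, with status at two visits from a latent normal with assumed correlation 0.3, 0.5 or 0.7. The no-effect rates assumed in both arms were 25%, 40%, 50% and 30/50%. Setting A has 80 per arm, with 12% interrupters set to failure at both visits or at Week 4 only. Setting B has no dropout and 72 or 80 per arm. Each cell gives the direct 2×n reading, then the Week 4 2×2.

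| Assumed % at ≤1, Week 2/Week 4 | A | B |
|---|---|---|
| No effect | 0.0–1.6% / 4.5–5.3% | 0.0–1.4% / 4.5–5.7% |
| 50/50 vs 25/25 | 0.1–1.0% / 85–86% | 0.1–0.9% / 88–91% |
| 70/70 vs 35/35 | 0.0–0.4% / 98% | 0.0–0.3% / 99–100% |
| 40/60 vs 20/40 | 2–5% / 60–61% | 2–5% / 69–72% |
| 30/60 vs 15/30 | 0.5–1.7% / 93% | 0.3–1.5% / 96–97% |
| 40/70 vs 40/40 | 25–32% / 92% | 26–34% / 96–97% |

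**A valid alternative.** Classifying each child by the number of visits at 1 or below (0, 1 or 2) gives a 2×3 table. Under setting A it rejects in 4.7–5.3% of trials with no effect. Its power is 70–100% in the four non-diverging scenarios and 49–54% in the diverging one. So two valid tables also differ, and the result depends on which is meant.

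**The case against.** The strongest reply is that the text never says the cells hold only children at 1 or below. It speaks of group differences in a number of patients, and the rule that interrupters are failures makes sense only if failures have a cell. That points to one status per child and a valid test. Section 13.2.2 also defers further detail to a Statistical Analysis Plan, and no such text is among the documents, so the definition may have been settled there.

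Much of this stands. A reader might infer that the plan certainly commits the trial to an invalid test. The documents do not support that, because the cell contents are unstated and the failures rule pulls the other way. It remains true that no valid table matches the stated dimensions: a table per visit is 2×2, not a table whose width counts observations, and counting visits at 1 or below gives n + 1 columns. A deferral of detail also does not correct a test already named in the protocol.

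The simulation has limits too. It covers one reading (arm by two visits). Symptom columns, score categories or baseline as a third observation were not simulated. Setting A keeps interrupters as failures at both visits in the full 80. Under the ITT definition this fits only children who stopped before Week 2 but still had a post-baseline TSS. Setting B has no dropout and leads to the same conclusion.

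**Conclusion.** The concern holds, at minor size. That the table is undefined is firm. That the test fails to compare the proportion reaching 1 or below holds on the most direct reading, which is likely but not certain. The zero statistic under proportional counts is exact. The power figures are illustrations under assumed rates and correlations and are not estimates for this trial.

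Two further inferences should be resisted. One is that the wording can never produce a false-positive claim: the low no-effect rejection rates were shown for the two-visit reading only. If the nine symptoms were instead each tested at two visits, there would be 18 tests, and if these were independent the chance of at least one p-value below 0.05 would be 1 − 0.95^18 = 60%. The other is that the trial's main conclusion is at risk. This is one secondary endpoint. The primary t-test on TSS change and the sample size do not use this table, and Section 13.2.2 plans frequencies or contingency tables for categorical data in any case.

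**What to change.** In Section 13.2.2 and the synopsis, replace the 2×n wording with a 2×2 chi-square of treatment group by reached or not reached a score of 1 or below. Give each child one status per visit, count treatment interrupters as failures, and do the test separately at Week 2 and at Week 4. This is the form the plan already uses for responders, who are tested at both weeks. Naming one visit as the main one is optional and is my suggestion, not something the plan does for responders.

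In the same edit, state:

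- whether a child must be at 1 or below on all nine symptoms, or whether each symptom is evaluated alone;
- whether the cut-off applies to the 12-hour score, the two-week score or their mean;
- if the analysis is symptom by symptom, that each symptom has its own 2×2 and that these results are descriptive or exploratory.

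Carry the same text into the SAP. The cost is wording only. No new data, visits or patients are needed.
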